8.	ASSES	SSING AND REPORTING OF ADVERSE EVENTS	15
	8.1.	Adverse Events (AE)	15
	8.2.	Adverse Drug Reaction (ADR)	15
	8.2.1.	Serious Adverse Event or Serious Adverse Reaction (SAE/SAR)	16
	8.3.	Suspected Expected Serious Adverse Reaction (SESAR)	17
	8.4.	Suspected Unexpected Serious Adverse Reaction (SUSAR)	17
	8.5.	Recording of Adverse Events	17
	8.5.1.	Definition of Adverse Event intensity	18
	8.5.2.	Definition of Adverse Event causality	18
	8.6.	Reporting of Serious Adverse Events	19
	8.7.	Exemption from expedited reporting	19
	8.8.	Adverse Event/Reaction follow-up procedures	19
9.	STUDY	Y SCHEDULE	20
	9.1.	Procedures at Each Visit	20
	9.2.	Assessment of Compliance	21
	9.3.	Risk assessment and Precautionary Measures	21
10.	STUDY	Y AND TREATMENT DURATION	21
11.	STATIS	STICS	22
12.	ACCES	SS TO SOURCE DATA / DOCUMENTS	22
	12.1.	Source Data	22

	12.2.	Source Documents2	22
	12.3.	Direct Access	22
13.	QUALITY CONTROL AND QUALITY ASSURANCE		23
	13.1.	Quality Control2	23
	13.2.	Study Monitoring2	23
	13.3.	Quality Assurance2	23
	13.4.	Inspection2	23
	13.5.	Audit2	23
14.	ETHIC	AL AND LEGAL CONSIDERATIONS2	24
	14.1.	Ethical Considerations2	24
	14.2.	Independent Ethics Committee (IEC) / Institutional Review Board	
		(IRB)2	24
	14.3.	Informed Consent2	24
	14.4.	Modification of Protocol2	24
	14.5.	Conduct of Study2	25
	14.6.	Personal Data and Data Protection2	25
	14.7.	Data Handling and Record Keeping2	25
	14.7.1.	Completion of Case Report Forms2	25
	14.7.2.	Archiving2	26
	14.8.	Confidentiality2	26
	14.9.	Responsabilities2	26
15.	FINAL I	REPORT AND PUBLICATION POLICY2	26
16.	SIGNA	TURES	27

PROTOCOL SUMMARY / SYNOPSIS

Coordinating Institution (Academic Study)	FSNN – Foundation for the Study of Nanoneurosciences and Neuroregeneration	
Title	E fficacy and S afety of C erebrolysin in the Treatment of A phasia after Acute Ischemic S troke (ESCAS)	
Study Code	ESCAS	
Study Locations	Spitalul Clinic Județean de Urgență Cluj-Napoca	
	Institutul RoNeuro Cluj-Napoca	
Investigational Medicinal Product	Cerebrolysin Solution for Injection (CRB)	
Name of Active Substance	Cerebrolysin Concentrate	
Phase	IV	
Indication	Acute Ischemic Stroke	
Study Design	Exploratory, prospective, randomized-controlled, double-blinded	
Study Duration	Study start: 05/2020 Study end: 05/2022	
Sample Size	N=120 • Group 1 – Cerebrolysin N = 60 • Group 2 – Placebo N = 60	
Primary Objective	To assess the efficacy of Cerebrolysin and Speech Therapy versus Placebo and Speech Terapy at 30 , 60 and 90 days after baseline using the Western Aphasia Battery (Romanian translated version).	
Secondary Objectives	 To assess the efficacy of Cerebrolysin and Speech Therapy versus Placebo and Speech Terapy at 30, 60 and 90 days after baseline using measures of motor, neurological and global functional outcome (NIHSS, BI, mRS). To evaluate the safety of Cerebrolysin and Speech Therapy versus Placebo and Speech Terapy at 30, 60 and 90 days after baseline. 	
Primary Variables	Western Aphasia Battery	
Secondary Variables	Demographics (including education) Medical history NIHSS modified Rankin Scale Barthel Index	
Safety Variables	Adverse Events (AE) Severe Adverse Events (SAE)	

Inclusion Criteria	 Radiologically (CT or MRI) and clinically confirmed diagnosis of acute ischemic stroke in the left MCA territory; Broca or mixed non-fluent aphasia, including transcortical motor aphasia" Inclusion between 3-5 days post stroke; Right-handedness; Romanian as language of daily use; Signed informed consent.
Exclusion Criteria	 Prior symptomatic ischemic or hemorrhagic stroke; Severe comprehension deficit that may compromise informed consent or understanding of instructions: fluent aphasias (ex. Wernicke aphasia); global aphasias. Preexisting neurodegenerative or psychiatric disease; Epilepsy or EEG-documented epileptic discharges; Severe chronic renal or liver failure; (AST, ALT > 4 times normal values, creatinine > 4); Life-threatening diseases; Auditory or visual deficits that cannot be corrected and might impair testing.
Visit Schedule	Visit 1 - Day 0 - Baseline 3-5 days post-stroke Demographics Medical history Western Aphasia Battery NIHSS Visit 2 - Day 30 ± 3 Western Aphasia Battery NIHSS Barthel Index modified Rankin Scale Adverse Events (AE) Severe Adverse Events (SAE)
	Visit 3 - Day 60 ± 3 • Western Aphasia Battery • NIHSS • Barthel Index • modified Rankin Scale • Adverse Events (AE) • Severe Adverse Events (SAE)
	Visit 4 - Day 90 ± 3 Western Aphasia Battery NIHSS

	Barthel Index
	modified Rankin Scale
	Adverse Events (AE)
	Severe Adverse Events (SAE)
Investigational Product	 Cerebrolysin Solution for Injection (CRB): 30 ml diluted with 0.9% saline solution to a total solution of 250 ml, administered by IV infusion
Reference Product	250 ml 0.9% saline solution administered by IV infusion
	Procedural i.v. administration blinding will be enforced for both therapeutic products.
Treatment Schedule	Eligible patients with aphasia will be divided into two groups:
	 Control group - patients receiving NaCl procedural placebo and speech therapy for 1h per day during the study period (30 treatment days). Treatment group – patients receiving: 30ml Cerebrolysin/Day + Speech Therapy (1h/day), 30 days during the study period;
	Treatment Cycle 1 – 30 ml Cerebrolysin/saline and ST for 2 x 5 days (2 weeks) Study days 1 – 14 30ml Cerebrolysin/saline i.v.
	1h Speech Therapy
	Treatment Cycle 2 – 30 ml Cerebrolysin/saline and ST for 2 x 5 days (2 weeks) Study days 29-42 30ml Cerebrolysin/saline i.v. 1h Speech Therapy
	Treatment Cycle 3 – 30 ml Cerebrolysin/saline and ST for 2 x 5 days (2 weeks) Study days 57-70 30ml Cerebrolysin/saline i.v. 1h Speech Therapy

1. EVALUATION METHODS

Western Aphasia Battery

Western Aphasia Battery (WAB) is an instrument for assessing the language function of adults with suspected neurological disorders as a result of a stroke, head injury, or dementia. There is an updated version, the Western Aphasia Battery-Revised (WAB-R). It helps discern the presence, degree, and type of aphasia. It also measures how the patient performed on the test to provide a baseline so they can detect changes throughout their time in therapy. This also allows to see the patient's language strengths and weaknesses so that they can figure out what to treat, and lastly, it can infer the location of the lesion that caused aphasia. The WAB targets English speaking adults and teens with a neurological disorder between the ages of 18 and 89 years old. The WAB tests both linguistic and non-linguistic skills. The linguistic skills assessed include, speech, fluency, auditory comprehension, reading and writing. The nonlinguistic skills tested include drawing, calculation, block design and apraxia. This study will use a Romanian linguistically validated version of WAB.

NIH Stroke Scale

The NIH Stroke Scale assesses neurologic deficit and is a 15 items scale that covers the level of consciousness, gaze, visual fields, facial palsy, motor functions, limb ataxia, aphasia, dysarthria and extinction and inattention. The NIHSS is observer-rated and takes 5-8 min to complete. Items have 3- to 5-point response scales, scored from 0 to 4 with higher score indicative of more severe disability. In case of patient death, the worst score possible will assigned. The NIHSS will be used to assess the severity of the stroke at baseline as well as in the follow-up examinations as a measure of neurological function deficit.

Modified Rankin Score

The Modified Rankin Score is a functional outcome scale measuring global outcome. It is used for grading the outcome and the level of disability after a stroke. The Modified Rankin Score is a 7-point ordinal scale with a score of 0 indicative of no residual symptoms at all and the worst possible score of 6 which is assigned in case of death. The Modified Rankin Scale is observer rated and takes about 5 min to complete.

Barthel Index

The Barthel Scale/Index (BI) is an ordinal scale used to measure performance in activities of daily living (ADL). Ten variables describing ADL and mobility are scored, a higher number being a reflection of greater ability to function independently following hospital discharge. Time taken and physical assistance required to perform each item are used in determining the assigned value of each item. The Barthel Index measures the degree of assistance required by an individual on 10 items of mobility and self care ADL.

2. STUDY OBJECTIVES

This study shall assess the efficacy and safety of Cerebrolysin in the treatment of aphasia after acute ischemic stroke.

2.1. Primary Objective

It is the primary objective of this clinical study to assess the efficacy of Cerebrolysin and Speech Therapy versus Placebo and Speech Terapy at 30, 60 and 90 days after baseline using the Western Aphasia Battery (Romanian translated version).

2.1.1. Primary Variable

Western Aphasia Battery

2.2. Secondary Objectives

- To assess the efficacy of Cerebrolysin and Speech Therapy versus Placebo and Speech Terapy at 30, 60 and 90 days after baseline using measures of motor, neurological and global functional outcome (NIHSS, BI, mRS).
- To evaluate the safety of Cerebrolysin and Speech Therapy versus Placebo and Speech Terapy at 30, 60 and 90 days after baseline.

2.2.1. Secondary Variables

- Demographics (including education)
- Medical history
- NIHSS
- modified Rankin Scale
- Barthel Index

3. STUDY DESIGN

Exploratory, prospective, randomized-controlled, double-blinded, phase IV study

4. SELECTION AND WITHDRAWAL OF PATIENTS

4.1. Patient Inclusion Criteria

- Radiologically (CT or MRI) and clinically confirmed diagnosis of acute ischemic stroke in the left MCA territory;
- Broca or mixed non-fluent aphasia, including transcortical motor aphasia";
- Inclusion between 3 and 5 days post stroke;
- Right-handedness;
- Romanian as language of daily use;
- Signed Informed Consent

4.2. Patient Exclusion Criteria

- Prior symptomatic ischemic or hemorrhagic stroke;
- Severe comprehension deficit that may compromise informed consent or understanding of instructions: fluent aphasias (ex. Wernicke aphasia); global aphasias;
- Preexisting neurodegenerative or psychiatric disease;
- Epilepsy or EEG-documented epileptic discharges;
- Severe chronic renal or liver failure; (AST, ALT > 4 times normal values, creatinine > 4);
- Life-threatening diseases;
- Auditory or visual deficits that cannot be corrected and might impair testing.

4.3. Stopping and Discontinuation Criteria

4.3.1. Discontinuation Criteria related to the Study

- Insufficient recruitment
- Continuous serious protocol violation and deviation

4.3.2. Discontinuation Criteria related to the Patient

Patients will be advised in the Informed Consent Forms that they have the right to withdraw from the study at any time without prejudice, and may be withdrawn at the Investigator's / Coordinator's discretion at any time. In the event that a patient drops out of the study or is withdrawn, the withdrawal / study termination page in the CRF should be completed. On the withdrawal page the Investigator should record the date of the withdrawal, the person who initiated withdrawal and the reason for withdrawal. Reasonable effort should be made to contact any patient lost to follow up during the course of the study in order to complete assessments and retrieve any outstanding data and study supplies.

Withdrawn by the Investigator due to

- Serious Adverse Drug Reaction
- Lack of efficacy
- Consent withdrawn
- Administrative reasons

The patient or his/her representative requested withdrawal due to

- An Adverse Event for which the Investigator did not consider removal from the study.
- Perceived insufficient therapeutic effect
- Withdrawal of consent for any other reason (data recorded until withdrawal will be kept in the database if not explicitly denied by the patient).

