9. STUDY SCHEDULE

9.1. Procedures at Each Visit

Visit 1 – Baseline – 3-5 days post-stroke (Study Day 1)

- Demographics
- Medical history
- Western Aphasia Battery
- NIHSS

Visit 2 – Study Day 30 ± 3

- Western Aphasia Battery
- NIHSS
- Barthel Index
- modified Rankin Scale
- Adverse Events (AE)
- Severe Adverse Events (SAE)

Visit 3 – Study Day 60 ± 3

- Western Aphasia Battery
- NIHSS
- Barthel Index
- modified Rankin Scale
- Adverse Events (AE)
- Severe Adverse Events (SAE)

Visit 4 - Study Day 90 ± 3

- Western Aphasia Battery
- NIHSS
- Barthel Index
- modified Rankin Scale
- Adverse Events (AE)

• Severe Adverse Events (SAE)

Treatment cycles

Treatment Cycle 1 – 30 ml Cerebrolysin/saline and ST for 2 x 5 days (2 weeks)

Study days 1 – 14 30ml Cerebrolysin/saline i.v. 1h Speech Therapy

Treatment Cycle 2 – 30 ml Cerebrolysin/saline and ST for 2 x 5 days (2 weeks)

Study days 29-42 30ml Cerebrolysin/saline i.v. 1h Speech Therapy

Treatment Cycle 3 – 30 ml Cerebrolysin/saline and ST for 2 x 5 days (2 weeks)

Study days 57-70 30ml Cerebrolysin/saline i.v. 1h Speech Therapy

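### Section 4.3.2 does not separate stopping infusions from leaving the study, nor require later WAB visits after withdrawal for lack of efficacy, so primary data may go missing because of the outcome

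*Protocol*

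**What the plan says.** Section 2.1 makes the WAB at 30, 60 and 90 days the basis of the primary objective. Section 4.3.2 governs how an individual patient leaves:

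- Patients may leave at any time, and they "may be withdrawn at the Investigator's / Coordinator's discretion at any time".
- The Investigator's reasons include "Lack of efficacy"; no criterion or threshold is attached. The patient's or representative's reasons include "Perceived insufficient therapeutic effect".
- On drop-out or withdrawal, "the withdrawal / study termination page in the CRF should be completed", with the date, the initiator and the reason. No final WAB is named.
- On retrieving data: "Reasonable effort should be made to contact any patient lost to follow up during the course of the study in order to complete assessments".
- Where the patient withdraws consent, "data recorded until withdrawal will be kept in the database if not explicitly denied by the patient".

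The visit list in section 9.1 has no early-termination visit. It places treatment cycles on study days 1-14, 29-42 and 57-70. Section 4.4 makes the study double-blind. Section 11 leaves the analysis to a statistical analysis plan that is not available here.

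**The concern.** Whether the primary outcome is measured should not depend on what it would have been. Section 4.3.2 recognises only departure from the study, and lack of efficacy is one of the grounds for it. The Day 30 visit falls at the start of cycle 2, and cycle 3 begins on day 57. A disappointing early course can therefore lead to removal before the Day 60 and Day 90 WAB. The patients lost this way would be those with the poorest recovery and, if the treatment works, more of them would be controls.

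Two things are at stake: attenuation of the treatment difference among those still observed, and power in a trial of 60 per arm. An analysis plan can choose how to handle missing scores, but it cannot require a visit. Who is assessed after infusions stop has to be settled in the protocol and the CRF.

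**Working it through.** **Step 1: the text.** For a patient whom the Investigator withdraws for lack of efficacy and who has not refused assessment, section 4.3.2 requires only the withdrawal page. The sentence on completing assessments names patients lost to follow-up, which is a different group. Section 9.1 adds nothing for withdrawn patients. The remaining WAB visits are thus neither required nor forbidden.

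**Step 2: inputs.** From the protocol: 60 per arm, WAB at Days 30, 60 and 90, one blinded rule for both arms. It states no exit rate, effect size, SD, alpha or power, so there is no figure of its own to reproduce. Everything below is assumed: scores in SD units, true Day 90 effect δ = 0.5, share q = 10-20% of controls leaving for poor early response, the same cut-off in both arms, correlation ρ between early response and Day 90 score, and fraction f of the effect already present at exit.

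**Step 3: completers-only difference.** With c = Φ⁻¹(q):

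- control mean = ρ·φ(c)/(1 − q)
- active mean = δ + ρ·φ(c − fδ)/(1 − Φ(c − fδ))

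Worked case, q = 0.10, f = 1, ρ = 0.6: c = −1.282, so φ(c)/(1 − q) = 0.1755/0.90 = 0.195. In the active arm c − δ = −1.782, giving 0.0816/0.9626 = 0.085 and 3.7% exits. Difference = 0.5 + 0.6 × (0.085 − 0.195) = 0.434, a 13% shrinkage.

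| Effect present at exit | q | ρ | Active-arm exits | Completers' difference | Shrinkage |
|---|---|---|---|---|---|
| one third | 10% | 0.6 | 7.4% | 0.474 | 5% |
| one third | 20% | 0.7 | 15.7% | 0.454 | 9% |
| all | 10% | 0.6 | 3.7% | 0.434 | 13% |
| all | 20% | 1.0 | 9.0% | 0.328 | 34% |

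The last row needs early response to determine the Day 90 score exactly, so it is an upper bound. With δ = 0 the two arm means are identical and the difference is 0.

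**Step 4: does a better analysis help?** A simulation with 400,000 patients per arm used correlation 0.7 between visits and an effect of δ/3 at Day 30, 2δ/3 at Day 60 and δ at Day 90. It compared completers only with a regression on the Day 30 WAB. For δ = 0.5 and control exits of 5/10/20%:

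- Exit driven by the observed Day 30 WAB: completers 0.48/0.47/0.46; model 0.50 throughout.
- Exit driven by the unobserved Day 60 state: completers 0.47/0.45/0.42 (shrinkage up to 17%); model 0.49/0.48/0.47.
- δ = 0: every estimate within 0.003 of zero.

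**Step 5: power.** Power = Φ(δ/√(2/n) − 1.96) at two-sided 5% (assumed). For δ = 0.5:

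- n = 60: Φ(2.739 − 1.96) = 78%
- n = 54 (10% lost per arm): Φ(2.598 − 1.96) = 74%
- n = 48 (20% lost per arm): Φ(2.449 − 1.96) = 69%

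**The case against.** The strongest reply is that the protocol nowhere says withdrawn patients go unfollowed. A reader might infer that they are dropped, but the text is silent on them. The retrieval sentence comes directly after the withdrawal sentences and shows an intent to collect outcomes, and section 8.8 follows adverse events through the course of the study. This stands: the defect is a missing requirement, not a rule against follow-up.

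A reader might also infer that the primary comparison is biased. That does not follow. With no true effect, one blinded rule acting equally on both arms leaves no bias, so what is modelled here is attenuation and not a false positive. If exit depends only on the Day 30 WAB, which is a scheduled assessment, a model using that score removes the bias, and the unseen analysis plan may specify one. Withdrawals for reactions to treatment could also push the estimate the other way.

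Finally, a patient's own reason for leaving cannot be struck out; section 4.3.2 rightly protects the right to go. The point therefore rests on the Investigator's reason and on the absence of continued assessment for patients who would still accept it.

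None of this answers the core. Silence permits outcome-dependent gaps, and an analysis plan cannot recover scores that were never taken.

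**Conclusion.** The concern holds as a risk. Section 4.3.2 merges stopping infusions with leaving the study, lets the Investigator withdraw a patient for lack of efficacy, and does not require the remaining WAB visits afterwards. Missing primary data can therefore depend on the primary outcome.

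The size cannot be fixed from the protocol. Under the assumptions above, attenuation among completers is about 5-9% with one third of the effect present at exit and correlation 0.6-0.7. The 13-34% range assumes that the whole Day 90 effect is already present at exit, with correlation 0.6-1.0. That is hard to square with a schedule in which only cycle 1 and the start of cycle 2 precede the Day 30 visit, so it should be read as a ceiling. The 10-20% exit rate is itself an assumption, and real exits may be fewer.

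Should-fix: the trial is exploratory and the number affected may be small, but the change is cheap.

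**What to change.** In section 4.3.2 and on the CRF, define two events, stopping study infusions and leaving the study, each with its own date and reason. Leave the reasons for stopping infusions and the patient's right to withdraw as they are. State that patients who stop infusions, including those withdrawn by the Investigator for lack of efficacy, are asked to attend the planned Day 30, 60 and 90 WAB, NIHSS, Barthel Index, mRS and adverse event assessments unless they withdraw consent to assessment. Extend the sentence on completing assessments to cover them.

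The cost is protocol wording, one CRF page, and visits that are already planned for what may be only a few patients. No additional patients are needed, and no rule on when treatment stops is changed.

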4.4. Randomisation, Blinding and Unblinding

This study will be performed under double-blind conditions to keep investigators, other study personnel and patients blinded to treatment allocation. Cerebrolysin is an amber-colored solution; therefore, colored infusion lines will be used for drug administration.

A set of envelopes for each patient enrolled should be distributed to the study nurse preparing the ready-to-use-infusion solution. These nurses are only responsible for the preparation and administration of infusion solutions, and they should not be involved in any further study-related procedures. This person should not be allowed to disclose any information about treatment allocation. A treatment envelope should not be opened until the patient's first ready-to-use-infusion has been prepared.

Patients meeting in- and exclusion criteria will obtain a random number corresponding to the random list generated in advance by a biometrician selected by the Coordinator. Based on the random list sealed, opaque randomization/emergency envelops will be provided as follows:

- To the study center to break blinding if reasonable suspicion of harm to the patient exists
- To the person assigned to prepare the ready-to-use-infusion
- To the study coordinator

On opening, the randomization/emergency envelopes are dated (date, hour) and signed by the person who has opened the envelope. The Investigator should promptly document and explain to the Coordinator any premature unblinding of the Investigational Product(s). The whole study will be unblinded after closure of the database and determination of the analysis populations.

5. INVESTIGATIONAL PRODUCTS

The Investigational Products will be made available by the Coordinator (FSNN)

5.1. Name and Description of the Investigational Products

Cerebrolysin Solution for Injection

5.1.1. Dosage, Formulation and Administration

 30 ml diluted with 0.9% saline solution to a total solution of 250 ml, administered by IV infusion

5.2. Packaging and Labelling

The investigational product and the reference product will be packaged and labelled for use in clinical trial according to GMP Annex 13 and local legislation.

5.3. Storage

CRB should be kept and stored under 25 degrees Celsius, in its original package.

All supplies must be kept in a locked place, inaccessible to unauthorised persons until they are delivered to the individual patient.

5.4. Investigational Product Accountability and Destruction

The amount of used medication will be recorded in the CRF. All unused medication will be counted and documented and unused investigational products will be destroyed upon completion of accountability.

6. CONCOMITANT MEDICATION

Not allowed concomitant medication: monoamine oxidase inhibitors, antipsychotic drugs or nootropic molecules.

All concomittant medications and therapies will be recorded in the CRF.

7. DEFINITION OF THE PRIMARY AND SECONDARY VARIABLES

7.1. Primary Variable

Western Aphasia Battery

Western Aphasia Battery (WAB) is an instrument for assessing the language function of adults with suspected neurological disorders as a result of a stroke, head injury, or dementia. There is an updated version, the Western Aphasia Battery-Revised (WAB-R). It helps discern the presence, degree, and type of aphasia. It also measures how the patient performed on the test to provide a baseline so they can detect changes throughout their time in therapy. This also allows to see the patient's language strengths and weaknesses so that they can figure out what to treat, and lastly, it can infer the location of the lesion that caused aphasia. The WAB targets English speaking adults and teens with a neurological disorder between the ages of 18 and 89 years old. The WAB tests both linguistic and non-linguistic skills. The linguistic skills assessed include, speech, fluency, auditory comprehension, reading and writing. The nonlinguistic skills tested include drawing, calculation, block design and apraxia.

